5.4.3 Height follow-up period

Patients completing or discontinuing Genotropin therapy will be followed up to document body heights from the completion or discontinuation of Genotropin therapy to the completion of investigation or until reaching adult height (final assessment). The follow-up period for each booklet will correspond to each fiscal year.

Note: "The date of final assessment" in each booklet of case report will be the date of final assessment in the corresponding fiscal year.

Note: The completion of treatment is defined as the completion of Genotropin therapy for the therapeutic objective initially intended at the commencement of treatment being judged as cured etc.

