6.8. Height follow-up after completion or discontinuation of Genotropin therapy

"Height Follow-up Form" will be used to collect data concerning body height in patients completing or discontinuing Genotropin therapy, and meeting the following criteria.

- Patients not switching to other drug product
- Patients not reaching adult height (final height)

[1] Date on which height follow-up is completed

[2] Height (to the first decimal place), and weight (to the first decimal place)

[3] Bone age

[4] Pubescence

[5] Future treatment strategy

Note: Any occurrence of adverse event during the height follow-up period should be separately investigated in details as determined necessary by Sponsor.

7. Analysis plan

Statistical analysis on safety and efficacy shall be performed; the results of which shall be posted in scientific journal, and reported at academic conferences and through research activities. In no event shall the investigator inquire Sponsor to perform statistical analysis for this investigation without confirming with Japan Genotropin Advisory Board in advance.

8. Discontinuation

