5.3. Other Analysis Sets

Set of patients who reached adult height (near final height).

The set of patients who reached adult height (near final height) is defined as a set of patients in the efficacy analysis set for whom adult height (near final height) was measured. Adult height (near final height) is defined as height after the time point that any of the following conditions is met.

- a. Annual height velocity of less than 2 cm after the maximum growth by puberty.¹
- b. Bone age of 17 years or older for males and 15 years or older for females.¹
- c. Reason for discontinuation in patient's profile of "reaching adult height (near final height)" or "epiphyseal closure".

Set of patients who did not reach adult height (near final height).

The set of patients who did not reach adult height (near final height) is defined as a set of patients in the efficacy analysis set who meet all the following conditions at the discontinuation of treatment and for whom height was measured at least once on Day 91 after the discontinuation of treatment or later.

- a. No puberty.
- b. Annual height velocity of 2 cm or higher after the maximum growth by puberty.
- c. Bone age of less than 17 years for males and less than 15 years for females.
- d. Reason for discontinuation in patient's profile of "reaching the standard height," "growth rate," "preference of patient/parent(s)," "non-compliance," "discontinuation of public funding," "change in diagnosis," "poor clinical response," "adverse event," "laboratory abnormal," or "others".

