8.2.4.2. Change in Height SDS

The summary statistics of measured values of height SDS at each age will be calculated for the efficacy analysis set and eligible criteria set. The evaluation points are according to [Appendix A1.1](#) Definition of timing for visit 1. The change in height SDS will be plotted with a solid line for individual male and female patients separately, with age on the horizontal axis and height SDS on the vertical axis. The start of treatment will be indicated as ▲, pubescence as ●, and reaching adult height (near final height) as ▼. They will be plotted with a dotted line after the completion/discontinuation of treatment.

The same calculation will be performed to prepare plots in the same manner for the set of patients who reached adult height (near final height) and set of patients not reached.

The summary statistics of measured values of height SDS at each evaluation point and change from the start of Genotropin will be calculated for a set of patients who reached adult height (near final height). The 95% confidence interval of the mean of the change will be calculated. The evaluation points are according to [Appendix A1.2](#) Definition of timing for visit 2. The change in height SDS will be plotted with a solid line for individual male and female patients separately, with evaluation points on the horizontal axis and height SDS on the vertical axis. The start of treatment will be indicated as ▲, pubescence as ●, and reaching adult height (near final height) as ▼. They will be plotted with a dotted line after the completion/discontinuation of treatment.

The summary statistics of measured values of height SDS at each evaluation point and changes from the start of Genotropin will be calculated in the efficacy analysis set and eligible criteria set. The 95% confidence interval of the mean of the change will be calculated. The evaluation points are according to [Appendix A1.3](#) Definition of timing for visit 3. The change in height SDS will be plotted with a solid line for individual male and female patients separately, with evaluation points on the horizontal axis and height SDS on the vertical axis. The start of treatment will be indicated as ▲, pubescence as ●, and reaching adult height (near final height) as ▼. They will be plotted with a dotted line after the completion/discontinuation of treatment.

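### The SAP judges 'did not reach adult height' when treatment stops but lets 'reached' be met at any later time, so once two conflicting conditions are reconciled a child can be in both sets

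*SAP*

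**What the plan says.** SAP 5.3 defines two sets within the efficacy analysis set.

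- **Reached adult height:** "a set of patients in the efficacy analysis set for whom adult height (near final height) was measured". The time rule is: "Adult height (near final height) is defined as height after the time point that any of the following conditions is met". The three conditions are (a) annual velocity below 2 cm after the pubertal maximum, (b) "Bone age of 17 years or older for males and 15 years or older for females", and (c) a recorded stop reason of adult height or epiphyseal closure.
- **Did not reach adult height:** patients "who meet all the following conditions at the discontinuation of treatment and for whom height was measured at least once on Day 91" or later after stopping. The conditions include (a) no puberty, (b) "Annual height velocity of 2 cm or higher after the maximum growth by puberty", (c) bone age below the same limits, and (d) a stop reason from a list that covers, among others, family preference, non-compliance and reaching the standard height.

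Protocol 5.4.3 follows children who have stopped "from the completion or discontinuation of Genotropin therapy to the completion of investigation or until reaching adult height (final assessment". Protocol 6.8 admits to this follow-up those who have not switched product and are "Patients not reaching adult height (final height". The assessment schedule in Protocol section 6 collects height, weight, pubertal status and bone age during it.

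SAP 8.2.4.2 asks for the same by-age summaries and plots for the "set of patients who reached adult height (near final height) and set of patients not reached". SAP 8.2.4.1 and 8.2.4.5 to 8.2.4.7 do likewise for their own endpoints.

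**The concern.** The two labels read as complements, but the sets are judged at different times. One is fixed on the day treatment stops. The other stays open for as long as the child is measured. The protocol follows early stoppers towards adult height and records the data needed to show that they reached it.

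Two things are at stake.

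1. In the set labelled as not reached, the row for completion of height follow-up (Appendix A1.3) and the oldest by-age rows (Appendix A1.1) can mix adult heights with heights of children still growing, and the label is wrong for the former.
2. In the reached set, the change in height SDS from start of treatment to adult height (Appendix A1.2, with a 95% confidence interval) is a single summary over children treated until adult height and children who did their last growing off treatment. A reader of the table cannot tell the two apart. This second matter does not depend on the overlap and would remain if the sets were made exclusive.

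**Working it through.** The documents give no figure to reproduce, so the check is logical: apply both definitions to every possible type of child and see who falls where.

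**Inputs (SAP 5.3; Protocol 5.4.3 and 6.8).**

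- Pubertal state at stopping: prepubertal, pubertal before the growth maximum, or past the maximum (3 states).
- Annual velocity at least 2 cm, or below (2).
- Bone age below the limit, or not (2).
- Stop reason: on the not-reached list, on the reached list, or neither (3).
- Follow-up: no height from Day 91 on; such a height but no adult height; such a height and later an adult height (3).

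Combinations: 3 × 2 × 2 × 3 × 3 = 108.

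**Results under three readings of conditions (a) and (b) of the not-reached set.**

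| Reading | Enter not-reached | Of these, also in reached |
|---|---|---|
| All conditions literal | 0 | 0 |
| (b) counts as met before the pubertal maximum | 4 | 2 |
| (a) and (b) are alternatives | 6 | 3 |

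- *Literal.* A child without puberty has not passed a pubertal growth maximum, so (a) and (b) cannot both hold and the set is empty.
- *(b) met before the maximum.* The child is prepubertal (1 state), with either velocity (2), bone age below the limit (1), a listed reason (1) and a height from Day 91 on, with or without a later adult height (2): 1 × 2 × 1 × 1 × 2 = 4. The 2 with a later adult height are in both sets.
- *Alternatives.* Add children past the maximum with velocity of at least 2 cm: 1 × 1 × 1 × 1 × 2 = 2, giving 4 + 2 = 6. The 3 with a later adult height are in both sets.

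Under both workable readings, the children in both sets are exactly the not-reached children who later have an adult height measured. The counts are types of child, not patients. If the not-reached set excluded members of the reached set, the overlap would be 0 by construction.

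**Which tables are touched.** Appendix A1.3 is applied to the not-reached set for height SDS, height velocity and height velocity SDS (SAP 8.2.4.2 to 8.2.4.4) and includes the completion-of-follow-up row. Under Protocol 5.4.3, follow-up can end at adult height or at the end of the investigation, so that row can hold both kinds of height. Appendix A1.1 is applied to both sets by year of age, so adult heights would appear in the oldest rows.

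**On and off treatment in the reached set.** Membership has no on-treatment requirement. The individual plots change line style after treatment ends, so off-treatment growth is visible for each child. The A1.2 summary table has no such split.

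**The case against.** The strongest reply is that anchoring at discontinuation is deliberate: the set exists to describe growth after stopping, so later adult heights are expected content. The plots support this, since both sets' plots are to carry the adult-height marker. This stands as an account of purpose, but it leaves the label wrong. A name that says treatment was discontinued before adult height would serve that purpose better.

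It can also be said that the text as written gives no overlap, because the set is empty. That is true, but an empty set cannot be what was intended, and either repair brings the overlap in.

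A third reply is that everyone with a measured adult height is a legitimate descriptive population. That also stands. The on/off-treatment split is an addition to the overall row, not a replacement for it.

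A reader might infer more than the documents support:

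- *Every early stopper whose follow-up succeeds is counted twice.* No. Follow-up may properly end with the child still growing, and stop reasons such as death or loss to follow-up are not on the not-reached list.
- *The two sets are compared or added up.* No analysis in the readable text does either. SAP 4.1 makes all testing exploratory, and a child still growing on treatment would normally be in neither set.
- *The main efficacy result is affected.* SAP 6.2 lists its endpoints without ranking them, and some efficacy text is redacted.

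**Conclusion.** The mismatch in timing and the lack of an exclusivity rule are in the text. A child can be in both sets under either workable reading of conditions (a) and (b), and under the literal reading the not-reached set is empty. Pooling of on- and off-treatment growth in the A1.2 summary is a separate, smaller point.

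The number of children affected cannot be computed from the documents. If absence of puberty stays a requirement, a child must go through all of puberty off treatment within follow-up, so the planned 3 years (Protocol section 4) would yield few. The permitted extension, and the earlier-investigation data that SAP 2.1 includes for ongoing subjects, could add some. If (a) and (b) are alternatives, a child near the bone-age limit could overlap soon after stopping.

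A reader might size the A1.2 pooling as the share of early stoppers times their difference in gain. Assuming 10% to 30% and 0.3 to 0.8 SDS, that gives 0.10 × 0.3 = 0.03 to 0.30 × 0.8 = 0.24 SDS. Neither input is in the documents, and the product concerns on/off-treatment mixing, not double counting. It is an illustration, not an estimate.

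Severity: minor to moderate. The tables are descriptive, so the harm is a misleading label and an unclear denominator rather than a wrong test.

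**What to change.** 1. In SAP 5.3, reconcile conditions (a) and (b) of the not-reached set, for example by stating whether they are alternatives or whether (b) applies only to children past the pubertal maximum.
2. Rename that set: discontinued Genotropin before adult height.
3. Add a derived flag for members who later met an adult-height criterion. In that set's tables, show their adult heights separately from heights of children still growing.
4. Report the number in each set, and in both, in the disposition table (SAP 8.2.1).
5. Keep the overall A1.2 row for the reached set. Beneath it, add rows for on Genotropin until adult height and for stopped before adult height.

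The cost is SAP wording, one derived flag and a few extra table rows, all from data already planned for collection. The downside is smaller numbers, and so wider intervals, in the split rows; the overall row is unaffected.

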6.5. Examinations/tests (clinical laboratory/clinical course)

Results of the following parameters tested will be recorded until the completion of assessment period for each booklet; provided that Booklet 01 should include the results prior to the commencement of Genotropin therapy. Of the results of examinations and tests performed prior to the commencement of Genotropin therapy, those within 1 month prior to the commencement of Genotropin therapy should be recorded (including the date the Genotropin therapy is commenced).

- [1] Carbohydrate metabolism related tests (fasting or continuous glucose, HbA1c), serum lipid concentration (total cholesterol, triglyceride), thyroid function related tests (TSH, free T4), and IGF-I
- [2] Height (to the first decimal place), weight (to the first decimal place), and head circumference (to the first decimal place)
- [3] Pubescence
- [4] Bone age
- [5] Body composition

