7. HANDLING OF MISSING VALUES

Any missing data on the seriousness, measures taken, and outcome of adverse events will be handled as “unknown” in summarizing data.

Measured values outside the acceptable range (Appendix 1) at each evaluation time point of the efficacy endpoints and clinical laboratory parameters will be handled as missing and missing data will not be imputed.

The procedure to handle uncleaned data is described below.

- Items with missing data: Missing data will be handled as missing (“unknown” for the category of classification variables) for both tabulation and listing.
- Items with inconsistent data: Inconsistent data will be handled as missing for both tabulation and listing. In this regard, however, a data handling list will be prepared separately.
- No signature: Descriptions in the report form without signature of the contract physician (or with signatures of other physicians than the contract physician) will be handled as missing for both tabulation and listing. No date or inconsistent date in the signature date section (eg, date of signature before or after the start date of treatment) will be considered to indicate that there is no signature on the report form.

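### SAP 5.3 admits a child to the set that did not reach adult height only with a bone age below 17/15 at stopping, but ties no film to stopping and has no rule for a missing one

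*SAP*

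**What the plan says.** SAP 5.3 defines two sets within the efficacy analysis set.

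- **Reached adult height.** One condition is enough: "Adult height (near final height) is defined as height after the time point that any of the following conditions is met". The three routes are "Annual height velocity of less than 2 cm after the maximum growth by puberty", a bone age at or above 17 years (boys) or 15 years (girls), and a stopping reason of adult height or epiphyseal closure.
- **Did not reach adult height.** All conditions are needed, together with a later height: "meet all the following conditions at the discontinuation of treatment and for whom height was measured at least once on Day 91" or later. The conditions are (a) that puberty has not begun, (b) a yearly velocity of at least 2 cm past the pubertal growth peak, (c) as the bone-age limit, "Bone age of less than 17 years for males and less than 15 years for females", and (d) a stopping reason from a stated list.

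On collection of bone age, Protocol 6.5 says: "Results of the following parameters tested will be recorded until the completion of assessment period for each booklet". Bone age is one of the items listed there, and it appears again on the Height Follow-up Form (Protocol 6.8). Neither section sets a date for it. Protocol 8.2 asks in general terms for a suitable assessment at the end of therapy and does not name bone age. Protocol 5.6 allows data after treatment to be taken by telephone.

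On missing data, SAP 7 treats missing items as missing (or as an unknown category for classification variables). It says that out-of-range values of efficacy endpoints and laboratory parameters "will be handled as missing and missing data will not be imputed". The visit tables in SAP Appendix 1 do not list bone age.

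**The concern.** Condition c is worded as something the child must satisfy, under a rule that the set contains those "who meet all the following conditions at the discontinuation of treatment". A child with no bone age on record does not satisfy it on the natural reading. The reached set has no such weakness, because two of its three routes need no film.

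The SAP uses the same thresholds in the opposite way in 5.2 d. There, a bone age at or above 17/15 at the start of treatment removes a patient from the eligible criteria set, so a patient without a film stays in.

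Protocol 5.5.3 and 6.8 give height follow-up to children who have not switched product and have not reached adult height, with no bone-age condition. The protocol therefore collects post-treatment heights that the SAP may then leave out of the set meant to describe them.

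This is the only set in the visible SAP text restricted to children who stopped before adult height. It is used in 8.2.4.1 to 8.2.4.7 for height, height SDS, height velocity, velocity SDS, body weight SDS, BMI SDS and IGF-I SDS, with 95% confidence intervals for the mean change in most of these. Membership would depend partly on whether a film happened to be taken.

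**Working it through.** The plan states no figure to reproduce. The check is one of set logic, followed by an illustration of size.

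**1. Enumerate the possible situations at stopping.** The inputs are the SAP 5.3 rules:
- puberty and post-peak velocity, 4 combinations: no puberty; puberty with velocity not definable, below 2 cm, or 2 cm and above;
- bone age, 3 levels: below threshold, at or above it, missing;
- stopping reason, 3 levels: adult height or epiphyseal closure; on the list in d; lost to follow-up or death;
- height on Day 91 or later, 2 levels: yes, no.

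This gives 4 × 3 × 3 × 2 = 72 states, 24 for each bone-age level. A height after the qualifying time point is assumed for the reached set. These are counts of logical states, not of patients.

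**2. Apply the not-reached rule literally.** Condition a requires no puberty, and condition b requires a velocity after the pubertal maximum. No state meets both, so 0 of 72 qualify whatever the bone age. To isolate condition c, the remaining steps read a and b as alternatives. That is an assumption, not SAP text.

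**3. Compare a missing film with a film below the threshold.**

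| Bone age at stopping | States | Reached | Did not reach | Neither |
|---|---|---|---|---|
| Below threshold | 24 | 12 | 2 | 10 |
| Missing | 24 | 12 | 0 | 12 |

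The 12 reached states in each row are 6 with velocity below 2 cm (3 reasons × 2 height levels) and 6 more through the stopping reason (3 other puberty/velocity combinations × 2 height levels).

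The 12 missing-film states in neither set break down as follows:
- 6 fail because the reason is loss to follow-up or death;
- 3 have a listed reason but no Day-91 height;
- 1 has puberty with no definable post-peak velocity;
- 2 fail on the missing film alone.

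Those 2 have a listed reason, a Day-91 height, and either no puberty or a velocity of 2 cm or more.

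**4. Reword c so that only a recorded bone age at or above the threshold excludes.** Qualifying states rise from 2 to 4, the two added being those just described. No state falls in both sets before or after the change.

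**5. Illustrate the size.** The documents give no frequency of bone-age tests. Let p be the assumed share of otherwise qualifying children with a film at stopping. Of 100 such children, 100 × p remain. With an unchanged standard deviation, the confidence interval widens by 1/√p − 1.

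| Assumed p | Remaining of 100 | CI wider by |
|---|---|---|
| 0.9 | 90 | 5% |
| 0.8 | 80 | 12% |
| 0.6 | 60 | 29% |
| 0.5 | 50 | 41% |
| 0.3 | 30 | 83% |

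**The case against.** Bone age is not neglected in the plan. It is a listed item in every treatment booklet and on the Height Follow-up Form. SAP 5.3 sets no window, so an earlier value might be accepted. Nor does SAP 7 say that a missing value means a condition is not met, and its sentence on non-imputation concerns efficacy endpoints and laboratory parameters, not set membership. All of this is correct. It shows that the SAP leaves the classification open; it does not supply a rule that keeps the child in. Listing an item also does not guarantee a value, since Protocol 6.5 covers only tests that were done.

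A second objection is that condition c is not the binding defect, because a and b together empty the set first. That also stands. Repairing a and b would still leave the gap in c.

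Third, the investigation is exploratory (SAP 4.1) and the main summaries use the efficacy and eligible criteria sets, which do not depend on this rule. That limits the consequence to the analyses of early stoppers.

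A reader might infer that every child without a film falls out of both sets. The documents do not support that: velocity below 2 cm or the stopping reason admits a child to the reached set without a film. Nor are the two sets meant to be exhaustive. Children still on treatment, lost to follow-up or without a Day-91 height can be in neither, with or without a film.

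**Conclusion.** The point holds in a limited form. A child who stopped for a listed reason, has a height on Day 91 or later, and meets neither the velocity nor the stopping-reason route to adult height is in neither set if no bone age is on record. This rests on the natural reading of c as a positive requirement, and on a and b being repaired so that the set is not empty. Later follow-up data could still bring such a child into the reached set.

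The number affected is unknown. The losses of 10% to 70% and the interval widening of 5% to 83% in the illustration follow from assumed film rates and are not estimates for this study.

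A reader might also infer that young prepubertal children are the ones lost and that the set is tilted towards children near the end of growth. Nothing in the documents says who is likely to have a film, so the direction of any selection cannot be derived.

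The SAP should be changed before the final analysis. The main efficacy summaries are not undermined.

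**What to change.** In SAP 5.3, reword c as an exclusion in the manner of 5.2 d: no bone age at or above 17 years (boys) or 15 years (girls) on record up to the stop date, taking the most recent value, with a missing value not excluding the child. Keep the list of reasons in d and the Day-91 height requirement, so that the set does not widen for other reasons.

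Reconcile a with b, since both cannot be met under a rule that requires all conditions. State whether they are alternatives, and how a pubertal child without a definable post-peak velocity is classified.

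Repeat the results for this set in children with a recorded bone age, as a sensitivity analysis. Report the number of discontinued patients in neither set, by reason: no bone age if c is left as it stands, reason not on the list, no later height, velocity not definable.

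The cost is SAP wording, one derived flag, one repeat of existing tables and one count table; no new data are needed. The downside is that a few children with an advanced but unrecorded bone age may enter the set. The sensitivity analysis would show whether the results depend on including children without a film.
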